7.2 Methods and Timing for Assessing, Recording, and Analyzing Safety Parameters

See Table 3.

7.3 Adverse Events and Serious Adverse Events

Adverse Event (AE) definition: An adverse event (AE) is any unfavorable and unintended diagnosis, symptom, sign (including an abnormal laboratory finding), syndrome or disease which either occurs during the study, having been absent at baseline, or if present at baseline, appears to worsen. Adverse events are to be recorded regardless of their relationship to the study intervention.

Serious Adverse Event (SAE) definition: A serious adverse event (SAE) is one that meets one or more of the following criteria:

- Results in death
- Is life-threatening (places the subject at immediate risk of death from the event as it occurred; includes a suicide attempt or drug overdose)
- Results in inpatient hospitalization or prolongation of existing hospitalization
- Results in a persistent or significant disability or incapacity
- Results in a congenital anomaly or birth defect

An important medical event that may not result in death, be life threatening, or require hospitalization may be considered an SAE when, based upon appropriate medical judgment, the event

may jeopardize the subject and may require medical or surgical intervention to prevent one of the outcomes listed in this definition.

Study staff will record all reportable events with start dates occurring any time after informed consent is obtained at least until the final day of study participation. Each time participants attend yoga classes, we will inquire about injuries due to yoga. For all participants in either the open trial or pilot RCT, at Month 3 (end of intervention), study staff will administer the SAFTEE in order to inquire about the occurrence of AE/SAEs during the previous 3 months. This allows us to systematically assess number of adverse events, severity, and resulting impairment. Finally, any time a participant (or parent) reports an adverse event to any staff member, a research assistant will contact the participant or parent or both to ascertain information for recording of the adverse event. For adverse events ascertained by any of these three possible methods, the research assistant gets information on what happened, start and stop dates, severity, functional impact, interactions with healthcare professionals, perceived cause, and possible relation to study participation.

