There are fewer studies of *hatha* yoga in adolescents than in adults, and very few studies of the effect of yoga on mood. We were unable to find any studies that rigorously examined yoga in adolescents with clinically significant depression symptoms at baseline. Given yoga's promising results in adults, and presumed mediators, we believe that *hatha* yoga may be a useful and safe intervention for depression in adolescents. However, it is necessary to adapt existing *hatha* yoga manuals for use in depressed adolescents. Using the Participatory Action Research framework, we will adhere to step-wise guidelines for adapting manualized interventions [9] which include conducting separate focus groups with adolescents and parents; soliciting feedback from experts; making iterative revisions of an instructor manual, and conducting pilot open and randomized controlled trials. We will classify specific modifications (to be informed by focus groups and expert feedback) using the system proposed by Stirman [10] to facilitate adaptation by other research groups.

We will then conduct an open trial of *hatha* yoga for adolescents with depression, followed by a pilot randomized clinical trial of *hatha* yoga vs. group CBT for depression. We chose group CBT as this is an empirically supported treatment for depression in adolescents [11], and we plan to ultimately conduct an equivalency trial. In both trials in this project, adolescents will receive the active intervention (i.e., weekly classes) for a 12-week period. Twelve weeks was chosen because it is sufficient time for improvement in depression symptoms and to administer the comparison intervention, group CBT for depression. Adolescents will attend classes once per week as more often is likely impractical (although we will discuss this issue in focus groups). Adolescents will be asked to complete relevant homework regardless of whether they are in *hatha* yoga classes or CBT classes. Potential risks of both interventions include loss of privacy or breach of confidentiality, increased distress due to procedures, and ineffective intervention (i.e., lack of improvement in depression symptoms). Potential risks of yoga include mild physical injury.

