5.4 Adherence Assessment

Yoga Participant Adherence. To be considered adherent, a participant must attend 8/12 classes and engage in home practice at least 2 times per week for 8/12 weeks (as assessed via self-report).

CBT Participant Adherence. Participant adherence is defined as number of groups attended; we define "satisfactory" adherence as attending 8/12 groups.

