6. STUDY PROCEDURES

6.1 Schedule of Evaluations

Table 1. Schedule of Evaluations, Phase 1.

| Assessment | Phone Screening: (Day-30 to Day-1) | Baseline, Enrollment, Visit 1 (Day 0) |
|--|---------------------------------------|--|
| Inclusion/Exclusion | X | |
| PHQ-8 | X | |
| Informed Consent Form | | X |
| Demographics and Psychotherapy Practice Scale-Patient Depression Care Version | | X |
| Payment – Adolescent | | \$35 |
| Payment – Parent | | \$35 |

Table 2, Schedule of Evaluations, Phase 2 and Phase 3.

| Assessment | Type of Assessment | Phone Screening: (Up to 30 days before BL1) | Baseline 1, Visit 1 | Baseline 2; must occur with 14 days of BL1 | After initial class | Weekly M1, M2, M3 | M1 visit | M2 visit | M3 visit | M6 visit (Phase 3 only) | M9 visit (Phase 3 only)** |
|--|---------------------------|---|---------------------|--|---------------------|-------------------|----------|----------|----------|-------------------------|---------------------------|
| Inclusion/Exclusion (A) | Interview, pre-randomize. | X | X | | | | | | | | |
| Informed Consent Form (A/P) | Pre-randomize. | | X | | | | | | | | |
| Enrollment – Phase 2 | Interview, non-blind RA | | X | X | | | | | | | |
| Enrollment and Randomization – Phase 3 | Interview, non-blind RA | | | X | | | | | | | |
| CEQ (A) | Self-report, non-blind DB | | | | X | | | | | | |
| CSQ-8 (A/P) | Self-report, non-blind DB | | | | | | | | X | | |
| Qualitative Interview (A/P) | Interview, non-blind RA | | | | | | | | X | | |
| Homework Questionnaire (A) | Self-report, non-blind DB | | | | | X | | | | X | X |
| Injuries due to yoga (A) | Self-report, non-blind DB | | | | | X | | | | | |
| SAFTEE (A/P) | Interview, non-blind RA | | | | | | | | X | | |
| Pregnancy (A) | Interview, non-blind RA | | X | | | | X | X | X | | |
| Other Adverse Events | Interview, non-blind RA | | X | X | | X | X | X | X | X | X |
| QIDS-A-CR (A/P) | Interview, blind RA | | X | | | | X | X | X | X | X |
| BDI (A/P) | Self-report, blind DB | | X | | | | | | X | X | X |
| CIS (A/P) | Self-report, blind DB | | X | | | | | | X | X | X |

| Assessment | Type of Assessment | Phone Screening: (Up to 30 days before BL1) | Baseline 1, Visit 1 | Baseline 2; must occur with 14 days of BL1 | After initial class | Weekly M1, M2, M3 | M1 visit | M2 visit | M3 visit | M6 visit (Phase 3 only) | M9 visit (Phase 3 only)** | |

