7.1 Specification of Safety Parameters

Safety issues will be minimal in Phase 1 given that participation involves only a single focus group, no yoga classes, and no formal assessment of suicidality. However, should an issue arise (e.g., a voluntary report of suicide ideation from one of the adolescent participants), staff would manage it in the same way that they would manage it in Phases 2 and 3.

Please see Table 3 for a summary of safety issues, how they are assessed, when they are assessed, and relevant staff actions.

Table 3. Assessment and Management of Safety Issues, Summary, Phases 2 and 3.

| Safety Issue | How assessed | When Assessed in Phase 2/Phase 3 | Relevant Research Staff Actions |
|------------------------|--|---|---|
| Suicidality | QIDS, BDI, MINI Participant/parent report to research staff | B1, M1, M2, M3, M6*, M9* B1, M3, M6*, M9* Any point | Immediate clinical assessment as described in DSMP |
| Clinical deterioration | Change in QIDS score | M1, M2, M3, M6*, M9* | Immediate clinical assessment as described in DSMP |
| Injuries due to yoga | Structured self-report | Weekly during first 3 months | Follow until resolution; may result in changes to yoga instructor manual |
| Pregnancy | Single interview question | BL1 (exclusion) M1, M2 | Discontinuation from intervention |
| Other AEs | SAFTEE CASA Participant/parent report to research staff | M3 BL1, M3, M6*, M9* Any point | If related to study participation, follow resolution; potential changes to procedures particularly if AE is also unexpected |

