| Assess feasibility, acceptability, and safety of both the yoga intervention and the comparison group ** This is primary ** | See Table 5 for a complete list (Endpoints examined separately for main participants and study B participants; also examined separately for participants consented pre-COVID and post-COVID) | Descriptive statistics (see Table 5) and qualitative data analysis |
| Assess within-group changes on outcomes. The primary outcome will be depression symptom severity at post-intervention (M3). Secondary outcomes include depression severity at follow-up (9 months), and self-report of depression, functional impairment, anxiety, and sleep at post-intervention (M3) and 9 months. ** This is exploratory ** | Endpoint = post-intervention (M3) (Endpoints examined separately for main participants and study B participants; also examined separately for participants consented pre-COVID and post-COVID) | Within-subjects t-tests (e.g., from pre-intervention to post-intervention/M3). We will conduct analyses separately by treatment group. We will calculate effect sizes (Cohen's d) from pre- to post-treatment/M3, with corresponding confidence intervals. |
| Assess within-group changes on self-compassion and meta-cognitive awareness ** This is exploratory ** | Endpoint = post-intervention (M3) (Endpoints examined separately for main participants and study B participants; also examined separately for participants consented pre-COVID and post-COVID) | Within-subjects t-tests (e.g., from pre-intervention to M3). We will conduct analyses separately by treatment group. |

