9.1.2 Description of Assessment Instruments

Acceptability and Feasibility. Intervention credibility and patient expectations for intervention

success at baseline will be measured with the Credibility Expectancy Questionnaire (CEO) [17]; this is administered after their initial class. The Client Satisfaction Questionnaire (CSQ-8) [18] will be used post-treatment to assess satisfaction with treatment. We will also use qualitative responses to a detailed post-treatment interview to gain participants' and parents' feedback about intervention components and research procedures. Finally, it is critical that the amount of yoga practice at home be measured as accurately as possible. Participants will complete a yoga home practice questionnaire on a weekly basis. This tool was designed to capture both brief "micro" practice (e.g., focusing on breathing for a few minutes) as well as more extended home practice (e.g., engaging in a 15-minute asana routine). The tool will yield three indices of home practice: frequency of extended home practice, minutes of extended home practice, and frequency of micro home practice.

Participant safety. After each home practice questionnaire (i.e., weekly during the intervention period), we will ask participants and parents whether participants experienced any injuries as a result of yoga. At the end of the study intervention (M3), we will administer the Systematic Assessment of Treatment-Emergent Events – General Inquiry (SAFTEE) [19]. This allows us to systematically assess number of adverse events, severity, and resulting impairment. To assess pregnancy, the adolescent will be asked in private whether there is a possibility of pregnancy. If they report that they may be pregnant, either at baseline or during follow-up, they will be excluded from study participation as our yoga protocol is not modified for pregnancy. Finally, any time a participant (or parent) reports an adverse event to any staff member, a research assistant will contact the participant or parent or both to ascertain information for recording of the adverse event. For adverse events ascertained by any of these three possible methods, the research assistant gets information on what happened, start and stop dates, severity, functional impact, interactions with healthcare professionals, perceived cause, and possible relation to study participation. For more information and details on coding of AEs, please see DSMP.

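### The only repeated structured adverse event question concerns yoga injuries, so pooled harm counts are collected unequally by arm, and its trigger and respondent are stated inconsistently

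*Combined protocol and SAP*

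**What the plan says.** Sections 7.3 and 9.1.2 give three routes by which adverse events are found: a question on yoga injuries, the SAFTEE at month 3 (recalling the preceding 3 months), and anything a participant or parent reports to staff. The safety aim covers both arms. Table 4 states it as "Assess feasibility, acceptability, and safety of both the yoga intervention and the comparison group" and marks it primary.

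The yoga-injury question is described in four places:

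- Section 7.3: "Each time participants attend yoga classes, we will inquire about injuries due to yoga".
- Section 9.1.2: "After each home practice questionnaire (i.e., weekly during the intervention period), we will ask participants and parents whether participants experienced any injuries".
- Table 3 (Section 7.1): "Injuries due to yoga | Structured self-report | Weekly during first 3 months".
- Table 2 (Section 6.1): "Injuries due to yoga (A) | Self-report, non-blind DB", marked in the weekly column. The (A) means adolescent only.

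Table 2 also has an Other Adverse Events row. It is labelled an interview by the non-blind research assistant and marked weekly and at every visit, with no restriction by arm. The visit list in Section 6.2.4 words the same item as events that have been reported to the research assistants. Table 3 gives the sources for other adverse events as SAFTEE, CASA and reports from the participant or parent.

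Table 5 sets one adverse event target, drawn from SAFTEE and the yoga-injury item together: no serious adverse events or injuries related to participation.

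**The concern.** A repeated prompt finds more minor events than a single recall over 3 months. If one arm has such a prompt and the other does not, a combined count partly reflects how often people were asked. The item's scope is also narrow. Section 2.2 says "Potential risks of both interventions include loss of privacy or breach of confidentiality, increased distress due to procedures", yet neither arm has a clearly active, repeated adverse event question on distress in general.

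The attendance trigger in 7.3 works the other way within the yoga arm. A teenager who stays away because of an injury, or is hurt in home practice during a week without class, would not be asked that week. Section 5.2 treats home practice as essential to dose, so exposure continues in such weeks.

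These counts feed decisions. They determine whether the Table 5 target is met, may lead to changes in the yoga manual, go to the funder and the safety committee each year, and are meant to prepare a later yoga versus CBT trial. Section 7 already cites 19 yoga enrollees with no yoga-related adverse events in arguing that video classes add no risk. Such statements are only as good as the rule for asking.

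**Working it through.** The plan gives no figure for adverse event ascertainment, so there is none to reproduce. The check sets the sources side by side and then shows how two assumed sensitivities would act.

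**Step 1. Scheduled capture from baseline to month 3, by arm.**

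| Source | Yoga | CBT | What it covers |
|---|---|---|---|
| Yoga-injury question | 12 if weekly; number of classes attended under 7.3 | 0 | Injuries attributed to yoga |
| SAFTEE | 1 (M3) | 1 (M3) | General, structured |
| QIDS | 3 (M1, M2, M3) | 3 | Suicidality and deterioration, which 9.1.2 says are not necessarily adverse events |
| CASA | 1 (M3) | 1 (M3) | Mental health service use |
| Other Adverse Events row | Weekly, M1, M2, M3 | Same | General, but active or passive is unclear |
| Volunteered reports | Any time | Any time | General, passive |

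Only the first row differs by arm. SAFTEE-only counts are ascertained identically.

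**Step 2. Effect of pooling (illustration only).** Take an event type that both the weekly item and SAFTEE could catch, with equal true rates in the arms. Assume the weekly question detects 0.9 of events, SAFTEE recall detects a share s between 0.5 and 0.9, the two act independently, and the Other Adverse Events contact adds nothing.

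- Yoga detects 1 − (1 − 0.9)(1 − s). CBT detects s.
- s = 0.5: 0.95 / 0.50 = 1.9
- s = 0.7: 0.97 / 0.70 = 1.4
- s = 0.9: 0.99 / 0.90 = 1.1

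None of these sensitivities is in the documents. The item asks only about yoga injuries, so the ratio cannot be applied to adverse events in general. If the weekly other-event contact is an active question in both arms, the ratio moves towards 1.

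**Step 3. Effect of the trigger within yoga.** The attendance threshold in Section 5.4 is that "a participant must attend 8/12 classes" (with a separate home practice requirement). Under 7.3 such a participant goes unasked in 12 − 8 = 4 weeks, and 4/12 = 33%. Under the weekly reading it is 0/12. With w weeks asked and the same assumptions, the share of injuries missed after SAFTEE is (1 − 0.9 × w/12)(1 − s):

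| Classes attended | Missed, class-linked (s = 0.9 to 0.5) | Missed, weekly (s = 0.9 to 0.5) |
|---|---|---|
| 12 | 1% to 5% | 1% to 5% |
| 8 | 4% to 20% | 1% to 5% |
| 4 | 7% to 35% | 1% to 5% |
| 0 | 10% to 50% | 1% to 5% |

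**Step 4. Respondent.** Section 9.1.2 says "we will ask participants and parents whether participants experienced any injuries as a result of yoga". Table 2 lists the adolescent alone. Both cannot be followed.

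**The case against.** The strongest reply is that injury monitoring matched to exposure is sensible. Section 7 expects mild physical injury from yoga and no adverse events from CBT. The safety analysis is descriptive, the study is not powered for differences between arms, and the Table 5 target is absolute. Closer questioning in yoga makes that target harder to meet, which is conservative. All of this stands, and it is why the point concerns pooled counts and not a planned comparison.

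Three stronger readings are tempting, and the documents do not support them.

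- A reader might infer that CBT harms rest on one recall interview, counting 12 + 1 = 13 prompts in yoga against 1 in CBT. That ignores the Other Adverse Events row, which carries no arm restriction, as well as three QIDS assessments, CASA and volunteered reports.
- A reader might infer a definite multiple by which yoga harms would be inflated. Any such figure depends on an assumed recall rate and treats a yoga-injury question as if it captured all minor events. CBT participants have no assigned yoga exposure, so equal true rates of yoga injury are not a meaningful scenario.
- A reader might infer that injured absentees are missed. That follows from 7.3 alone. Section 9.1.2 and Tables 2 and 3 make the question weekly, Section 7.2 refers to Table 3 for timing, and the SAFTEE is attempted even after a participant leaves treatment.

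The reply does not settle whether the weekly other-event contact is an active question. It also leaves 7.3 in conflict with the other descriptions.

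**Conclusion.** The concern holds in a limited form. Only yoga has a clearly structured, repeated adverse event question, so counts that combine it with SAFTEE are ascertained unequally by arm; SAFTEE-only counts are not affected. The bias cannot be sized from the documents. Under the assumptions shown, for events that both instruments could catch, the apparent ratio would be 1.1 to 1.9, and this is illustrative only.

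The conflict over trigger and respondent is a plain inconsistency in the text. Its firm size is 4 of 12 weeks (33%) unasked for a participant at the 8-class threshold, if staff follow 7.3. The weekly reading has the greater support in the protocol. No planned test is invalidated; what is at stake is how far the descriptive safety record can be relied on in designing the next trial.

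**What to change.** 1. Reconcile Section 7.3, Section 9.1.2 and Tables 2 and 3, so that the yoga-injury question has one calendar-based trigger that does not depend on class attendance, and one stated respondent (adolescent, or adolescent and parent).
2. State that the weekly Other Adverse Events contact already in Table 2 is an active question, worded identically in both arms. It could go in the weekly electronic questionnaire held in the non-blind database. For example, it could ask about any new or worse physical or emotional problem that week and its perceived cause. Keep the yoga-injury follow-up for the yoga arm, and align Section 6.2.4 and Table 3.
3. In Table 5 and the reports, present adverse events from the common instruments (weekly question, SAFTEE) by arm, and yoga-specific injury reports separately.

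The cost is one item in an existing weekly form, a small burden on CBT participants, and more minor adverse events to code each week. If the question is introduced part-way through Phase 3, events collected before and after the change should be shown separately.

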In this study, we conduct assessments with both the adolescent and parent, typically at the same time. Both RAs are blind to treatment group at baseline, as it has not yet been assigned. The non-blind RA will conduct the randomization. For follow-up assessments, we have detailed in Table 2 above whether the blind or non-blind RA will conduct a particular assessment.

In reporting adverse events to the Independent Monitoring Committee, determination of “causal relationship” will be made by the non-blind PI only, as it may require knowledge of which intervention arm the participant is in. The standard Adverse Events Reporting Form of our IRB does not ask for intervention arm; thus risk of un-blinding from AE reporting is minimal.

Either PI can conduct suicide or other risk assessments. If the blind PI is conducting a risk assessment, she will remind the participant not to reveal the intervention arm. In the unlikely event that a risk assessment is needed during class and the blind PI needs to conduct the risk assessment, the non-blind RA will bring the participant to a neutral location for assessment.

The non-blind PI will meet with yoga instructors and CBT therapists for supervision. The *Protocol Template, Version 3.2*

instructor/ therapist adherence ratings will be conducted by the non-blind PI and RA.

We will keep a record of any instances of un-blinding. This record will be used to improve procedures for a larger clinical trial. After all data are collected and the database is locked, the blind PI may be un-blinded so as to contribute to data interpretation.

Participants and parents cannot be blind to study intervention. However, we will present both interventions (CBT or yoga) with equipoise to all participants in written materials and orally.

6.2.4 Follow-up Visits – Phases 2 and 3

For the purposes of targeting dates for an assessment, we will consider each month = 28 days (4 weeks exactly). For all follow-up assessments, research staff will make every effort to conduct the assessment within one week before or one week after the exact due date of the assessment. However, because all data can be analyzed with modern statistical methods regardless of whether it was collected inside that window, RAs will still collect data if possible even if it is later than that two-week window. We will record optimum date for the assessment (e.g., Enrollment + 84 days for M3 assessment) as well as the actual date of the assessment.

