curiosity subscale [27]. We will assess self-compassion with the 26-item Self-Compassion Scale (SCS)[28]. This scale can yield a general self-compassion score and has previously been used with adolescents [29].

Other assessments. Finally, we will use the International Physical Activity Questionnaire (IPAQ) [30], a self-report measure of physical activity. We have also adapted this scale to measure amount of yoga practice participants engaged in during the follow-up time period. We will assess antidepressant medication use with the interview-based Treatment Response to Antidepressant Questionnaire (TRAQ) [31]). We will use the Child and Adolescent Services Assessment (CASA)[32] interview to assess other mental health treatment. If a participant is engaged in psychotherapy but the participant and parent are unclear as to whether it is CBT, we will use the Psychotherapy Practice Scale-Patient Depression Care Version [33] to help determine whether it is likely that the participant is engaged in CBT. This questionnaire will be modified to include some open-ended questions about the nature of the participant's psychotherapy. We will use the Perceived Cohesion scale to assess group cohesion.

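### After Month 3 no named instrument asks about yoga injuries or general physical adverse events, although events are recorded to the last study day and yoga practice is still measured

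*Combined protocol and SAP*

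**What the plan says.** Section 7.3 commits staff to "record all reportable events with start dates occurring any time after informed consent is obtained at least until the final day of study participation", whether or not an event is related to the intervention. It then names three ways of finding events: an injury question each time a participant attends a yoga class, the SAFTEE, and whatever a participant or parent reports to staff.

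- **SAFTEE.** Table 2 (Section 6.1) has a single mark, at M3. Section 7.3 says that staff "administer the SAFTEE in order to inquire about the occurrence of AE/SAEs during the previous 3 months".
- **Yoga-injury item.** Table 3 (Section 7.1) gives its timing as "Weekly during first 3 months". Table 2 marks it only in the weekly column, and Section 9.1.2 ties it to the weekly home-practice questionnaire of the intervention period.
- **Yoga exposure after M3.** The yoga practice interview and the homework questionnaire are both scheduled at M6 and M9. Of the IPAQ-based scale, Section 9.1.2 says that the team has "adapted this scale to measure amount of yoga practice participants engaged in during the follow-up time period".
- **Other adverse events.** Table 2 types this row as an interview by the non-blind research assistant, with marks at M6 and M9. The visit list in Section 6.2.4 describes it as other events that are reported to the research assistants. Table 3 lists three sources: the SAFTEE at M3, the CASA interview at BL1, M3, M6 and M9, and participant or parent report at any time.

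**The concern.** Of the three methods in Section 7.3, only spontaneous report clearly continues after M3. The plan goes on measuring yoga exposure in follow-up but stops asking about physical injury, which Section 7 gives as the only adverse event expected from yoga. Section 7 expects those injuries to be mild aches or pain, and mild events are the kind that people tend not to mention unless asked.

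Safety of both interventions belongs to the Phase 3 aim that Table 4 marks as primary. The safety target in Table 5 is that no serious adverse events or injuries are related to participation, and it names the SAFTEE and the yoga-injury item as its instruments. Both stop at M3. If the pilot reports no related physical events over the whole of participation, readers of the later non-inferiority proposal could not tell, for the follow-up period, an absence of events from an absence of questions.

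**Working it through.** No sample-size or power figure is involved. The check sets the safety schedule side by side and then counts days.

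**Step 1. What is asked at M6 and M9** (Tables 2 and 3, Sections 6.2.4, 7.3 and 9.1.2)

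| Harm | Instrument | Up to M3 | M6 / M9 |
|---|---|---|---|
| Suicidality | QIDS, BDI, MINI module | yes | yes |
| Clinical deterioration | change in QIDS | yes | yes |
| Mania/hypomania | MINI module | yes (M3) | yes |
| Mental health service use | CASA | yes | yes |
| Yoga injury | injury item | weekly | none |
| General adverse events | SAFTEE | M3 | none |
| Other adverse events | none named | yes | marked, content unclear |

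Two of these rows lose their instrument after M3: yoga injury and general adverse events. The psychiatric rows do not.

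**Step 2. Whether another entry fills the gap.** Section 9.1.2 describes the CASA as assessing other mental health treatment. On that description it would not pick up a strain or another physical event. For the other-adverse-events row, Table 2 says interview, Section 6.2.4 says events reported to staff, and Section 7.3 supplies no prompt beyond the three methods. The documents leave open whether anyone asks.

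**Step 3. Length of the gap.** Section 6.2.4 sets one month to 28 days and counts from enrollment.

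- M3 = 3 × 28 = day 84, which matches the plan's own example of enrollment plus 84 days.
- M6 = 6 × 28 = day 168. M9 = 9 × 28 = day 252.
- Followed to M6: 168 − 84 = 84 days; 84 / 168 = 50%.
- Followed to M9: 252 − 84 = 168 days; 168 / 252 = 67%.

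**Step 4. Sensitivity to visit timing.** Visits are aimed to fall "within one week before or one week after the exact due date of the assessment", so M3 is day 77 to 91, M6 is day 161 to 175 and M9 is day 245 to 259.

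- To M6: shortest gap 161 − 91 = 70 days (70 / 161 = 43%); longest 175 − 77 = 98 days (98 / 175 = 56%).
- To M9: shortest gap 245 − 91 = 154 days (154 / 245 = 63%); longest 259 − 77 = 182 days (182 / 259 = 70%).

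The conclusion does not depend on exact visit dates.

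**Step 5. Who is affected.** Phase 2 ends at M3, so it has no gap. Phase 3 is affected in Study A (34 adolescents) and in Study B (up to 20), which follows the same procedures. The M9 visit applies only to participants whose consent form is dated 12/1/2020 or earlier. The documents do not say how many these are.

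**The case against.** The strongest case for the plan is that recording events throughout while soliciting them systematically only during treatment is a coherent and common choice. The two do not contradict each other. Table 5 names its instruments, so its safety target can be read as covering the intervention period. The plan measures yoga practice after week 12 but prescribes none, and Section 7 describes the expected aches as arising during or shortly after classes. Table 2 does call the M6/M9 entry an interview. The data and safety monitoring plan, which the protocol cites for event coding, is not among the documents and may say more.

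Much of this stands. This is a design choice and not an error, and the interview label means one cannot say that nobody asks. What remains is that no instrument or prompt is named for that interview, that two other sections read as passive report, and that Table 5 does not limit its target to the first three months.

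Two stronger readings are tempting, and the documents do not support either.

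- A reader might infer that all harms in follow-up rest on volunteered reports. They do not: the QIDS, BDI, MINI modules and CASA continue at M6 and M9, Section 9.1.2 treats the QIDS as a safety assessment, and Table 3 counts the CASA as a source of adverse events.
- A reader might infer that a SAFTEE given early in the M3 window leaves injuries at the last yoga class unasked. Section 7.3 asks about injuries at every yoga class attended, whatever the SAFTEE date.

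**Conclusion.** The point holds for yoga injuries and general physical adverse events in Phase 3 follow-up. No named instrument asks about them for 84 of 168 scheduled days (50%) in participants followed to M6 and 168 of 252 days (67%) in those followed to M9. It does not extend to psychiatric harms, to the intervention period or to Phase 2. Separately, the M6/M9 entry for other adverse events is described inconsistently between Table 2 on one side and Sections 6.2.4 and 7.3 on the other.

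The conclusion assumes 28-day months counted from enrollment, the CASA as Section 9.1.2 describes it (its items are not shown), and nothing in the separate monitoring plan that adds an inquiry. The practical weight is modest, since serious injuries would probably come to light anyway. The loss is mainly in minor events and in how far a finding of no events can be trusted. The change is worth making because safety is part of the primary aim and the remedy is cheap.

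**What to change.** At M6, and at M9 for participants on the older consent form, have the non-blind research assistant give the existing yoga-injury item and the SAFTEE general inquiry, with recall running from the date of the last SAFTEE.

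Then make four places agree:
- **Table 2:** add the marks at M6 and M9, and state what the other-adverse-events interview consists of.
- **Section 6.2.4:** list both instruments under M6 and M9.
- **Table 3:** extend the timing of the injury item and the SAFTEE.
- **Section 7.3:** replace the single M3 administration with the full schedule.

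The cost is a short amendment and a few minutes at visits that already take place. The non-blind research assistant already conducts the yoga practice interview at those visits. The injury item already follows the home-practice questionnaire during treatment, and the homework questionnaire is given again at M6 and M9. Both safety instruments are already assigned to the non-blind side of data collection, so the blinded outcome ratings are unaffected. The downside is slightly longer M6 and M9 visits and more minor events to code. If the team prefers to leave solicitation at M3, the lesser remedy is to say so in Table 5 and to report follow-up injuries and physical events as spontaneously reported only.
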